5.3 Blinding

This study is not blinded.

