9 ADVERSE EVENT REPORTING

9.1 Definitions

9.1.1 Adverse Event

An AE is any untoward medical experience occurring to a subject during a clinical trial whether or not it is related to the study drug. An AE may include an intercurrent illness, injury, or any other concomitant impairment of the subject's health, as well as abnormal laboratory findings if deemed to have clinical significance. AEs may also include worsening of an existing symptom or condition or post-treatment events that occur as a result of protocol-mandated procedures.

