9.1.3 Expected Adverse Event

Adverse events associated with progression of PAH:

An expected event that is related to the progression of a subject's PAH is defined in Appendix D, Part A. All events that occur during the course of the study that are included on this list and felt to be related to progression of disease by the Investigator should NOT be recorded as AEs in the CRF as the most relevant PAH symptoms will be evaluated and recorded as an efficacy endpoint and all other events will be captured as disease related events. If the event is either serious or unusual with respect to intensity, frequency, or duration, OR there is a reasonable possibility that it may have been caused by study drug, it must be recorded as an AE in the CRF.

Adverse events known to be associated with treprostinil therapy:

An expected AE for UT-15C is defined as any AE that is defined in terms of nature, severity, or frequency in the current Investigators' Brochure and in Appendix D, Part B. When an adverse event may be attributed to the progression of pulmonary hypertension or UT-15C SR (e.g., listed in both Parts A and B) it must be recorded as an AE in the CRF if the event is either serious or unusual with respect to intensity, frequency, or duration, OR there is a reasonable possibility that it may have been caused by study drug.

Expected events attributable to UT-15C (e.g., listed in Part B only) must always be recorded as AEs in the CRF.

If an event listed in Appendix D Part A or B occurs during the conduct of the trial, it will not give rise to submission of an expedited safety report despite being considered serious and possibly attributable to the study drug, unless the United Therapeutics Medical Monitor, responsible for assessing the case considers it to be unusual (e.g., more severe than expected) and therefore reportable. The data regarding such events will always be recorded in the clinical study database, regardless of reportability.

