## 11.3 DISEASE RELATED EVENTS

The disease-related events reported during the TDE-PH-304 study will be listed, including subject number, previous study, and symptom. The summary will include the number (percent) of subjects who reported each symptom by previous study and overall.

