**12.2 LIST OF TABLES**

Table titles suggested here may be altered or edited as appropriate by the clinical data programmers while maintaining the original intent of the summary.

Table Number	Table Title
14.1.1	Summary of Subject Accountability
14.1.2	Summary of Disposition and Study Drug Exposure
14.1.3	Summary of Demographics
14.1.4	Summary of PAH History
14.1.5	Summary of Admission Criteria Violations
14.1.6.1	Summary of Study Drug Dosing by Previous Study and Overall
14.1.6.2	Summary of Study Drug Dosing by PAH Background Medication Use
14.1.6.3	Summary of BID to TID Transition
14.1.7.1	Summary of PAH Concomitant Medications Ongoing at Start of TDE-PH-304 Study
14.1.7.2	Summary of PAH Concomitant Medications Added During the TDE-PH-304 Study
14.1.7.3	Summary of PAH Medication Use by Class
14.1.7.4	Summary of Other Concomitant Medications
14.2.1.1	Summary of Six-Minute Walk Distance at Month 12 by Previous Study
14.2.1.2	Summary of Borg Dyspnea Score at Month 12 by Previous Study
14.2.1.3	Summary of Six-Minute Walk Distance at Month 12 by Treatment Assignment in Previous Study
14.2.1.4	Summary of Borg Dyspnea Score at Month 12 by Treatment Assignment in Previous Study
14.2.1.5	Summary of Six-Minute Walk Distance by PAH Medication Use
14.2.1.6	Summary of Borg Dyspnea Score by PAH Medication Use
14.2.1.7	Summary of Six-Minute Walk Distance by PAH Etiology
14.2.1.8	Summary of Six-Minute Walk Distance by Baseline WHO Functional Class
14.2.1.9	Summary of Six-Minute Walk Distance by Dosing Quartiles/ Tertiles
14.2.1.10	Summary of Six-Minute Walk Distance Achievement at Month 12
14.2.1.11	Summary of Six-Minute Walk Distance at Baseline by Achievement of At Least 380 Meters at Month 12

Table Number	Table Title
14.2.1.12	Summary of Clinical Events
14.3.1.1	Summary of Adverse Events
14.3.1.2	Summary of Adverse Events by System Organ Class
14.3.1.3	Summary of Serious Adverse Events
14.3.1.4	Summary of Serious Adverse Events Reasonably or Possibly Related to Study Drug
14.3.1.5	Summary of Adverse Events Reasonably or Possibly Related to Study Drug
14.3.1.6	Summary of Severe Adverse Events
14.3.1.7	Summary of Adverse Events Leading to Permanent Discontinuation of Study Drug
14.3.1.8	Summary of Disease Related Events
14.3.1.9	Summary of Adverse Events by UT-15C Exposure Time
14.3.2.1	Listing of Deaths
14.3.2.2	Summary of Deaths
14.3.2.3	Listing of Serious Adverse Events
14.3.4.1	Summary of Hematology Data

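### For PAH-progression symptoms the AE table is not an all-cause count, because events attributed to progression are tabulated separately and no planned output combines the two

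*Protocol*

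**What the plan says.** Protocol 9.1.1 defines an adverse event "whether or not it is related to the study drug". Protocol 9.1.3 then makes an exception for expected signs of PAH progression. Events on Appendix D Part A that are "felt to be related to progression of disease by the Investigator should NOT be recorded as AEs in the CRF". The most relevant PAH symptoms are to be recorded as an efficacy endpoint, and "all other events will be captured as disease related events". An override returns some events to the AE page: "If the event is either serious or unusual with respect to intensity, frequency, or duration, OR there is a reasonable possibility" of drug cause. Symptoms on both lists get the same test, in the sentence that begins "When an adverse event may be attributed to the progression of pulmonary hypertension or UT-15C SR (e.g., listed in both Parts A and B". Events on Part B alone are always AEs. Protocol 5.3 states: "This study is not blinded".

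SAP 11.2 summarises AEs by MedDRA preferred term and includes parent-study AEs for subjects who were on active drug there. SAP 11.3 handles disease-related events reported during TDE-PH-304, by symptom: "The summary will include the number (percent) of subjects who reported each symptom by previous study and overall". It does not mention MedDRA coding, event counts or dates.

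**The concern.** Adverse events are the first safety endpoint listed in protocol 2.2 and SAP 2.2. A reader who knows the definition in 9.1.1 will take Table 14.3.1.1 as all-cause incidence. For Part A symptoms it is not. Non-serious, unremarkable occurrences drop out when the investigator, who knows the subject is on drug, attributes them to progression and sees no reasonable possibility of drug cause.

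Reported incidence for these symptoms then depends partly on attribution habits. Those habits can differ between sites or previous studies, or shift over time as opinion about the drug changes. SAP 8.1 presents all summaries by previous study, and SAP 5 foresees interim outputs as often as yearly. A shift in attribution could therefore look like a difference or trend in safety when the events themselves had not changed.

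**Working it through.** The plan states no figure to reproduce. The check has three parts: the routing rule, the list of outputs, and what two separate percentages can say about their union.

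**1. Routing of a Part A symptom under protocol 9.1.3 (TDE-PH-304 period)**

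| Occurrence | Destination |
|---|---|
| Serious | AE |
| Unusual in intensity, frequency or duration | AE |
| Reasonable possibility of drug cause | AE |
| None of these, attributed to progression | Disease-related event, or efficacy endpoint for the most relevant PAH symptoms |
| None of these, attributed to neither progression nor drug | AE under 9.1.1 |

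Only the fourth row leaves the AE page. It depends on investigator judgement.

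**2. Outputs in SAP 12.2 to 12.4**

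- AEs alone: Tables 14.3.1.1 to 14.3.1.7, 14.3.1.9 and 14.3.2.3; Listing 16.2.7.1.
- Disease-related events alone: Table 14.3.1.8; Listing 16.2.7.3.
- Clinical events (SAP 10.2): death, discontinuation and added therapy, not symptoms.
- Both streams together: none.

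**3. Bounds**

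Let A be the percentage of subjects with the symptom as an AE in TDE-PH-304, and D the percentage with it as a disease-related event. If every occurrence goes to one of these two pages, the percentage with the symptom at all, U, satisfies

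max(A, D) ≤ U ≤ A + D.

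Example: A = 20% and D = 15% give U between 20% and 20 + 15 = 35%. A falls short of U as soon as one affected subject appears only in the disease-related stream. The sum overshoots when a subject appears in both.

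**4. Illustration (incidence and split are assumptions; the documents give neither)**

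One occurrence per affected subject, U = 20%, share p attributed to progression: A = 20(1 − p). At p = 0.25, A = 15%; at p = 0.75, A = 5%.

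Two occurrences per affected subject, each routed independently with p = 0.5: A = D = 20(1 − 0.5²) = 15%. The sum is 30%, against a true 20%.

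Poisson occurrences, each sent to the AE page with probability q: A = 1 − (1 − U)^q and D = 1 − (1 − U)^(1 − q). With U = 30%:

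| q | A | D | A + D |
|---|---|---|---|
| 0.25 | 8.5% | 23.5% | 32.0% |
| 0.5 | 16.3% | 16.3% | 32.7% |
| 0.75 | 23.5% | 8.5% | 32.0% |
| 0.9 | 27.5% | 3.5% | 31.0% |
| 1 | 30.0% | 0.0% | 30.0% |

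The direction is fixed by the routing rule. The size depends on q: at 0.9 the shortfall is 30 − 27.5 = 2.5 percentage points, and at 1 it is zero.

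**The case against.** Keeping expected disease events apart from AEs is a legitimate design, and the rule leans towards AE recording, since any one of three triggers is enough. For a symptom already listed as a treprostinil effect, a reasonable possibility of drug cause is easily conceded, so the AE table may be nearly complete for dual-listed symptoms. Serious events always become AEs and deaths have their own outputs. Both planned listings identify the subject, so an ever/never union could be built by hand for TDE-PH-304, and SAP 1 permits further analyses. All of this stands. It limits the size of the problem but does not supply the missing output, and nothing planned would show whether the shortfall is small.

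A reader might also infer three stronger things that the documents do not support.

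- That nearly every non-serious event of these terms in Table 14.3.1.5, "Summary of Adverse Events Reasonably or Possibly Related to Study Drug", would be drug-related by construction. An event attributed to neither progression nor drug is still an AE under 9.1.1, so this does not follow.
- That all of Table 14.3.1.1 rests on unblinded opinion. It includes parent-study AEs from subjects on active drug. Some of those parents were placebo-controlled, so those events may have been recorded blind, under instructions not reproduced here.
- That Table 14.3.1.8 is wrong to omit drug-attributed occurrences. That omission follows from what the table is defined to show.

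**Conclusion.** The point holds in limited form. For the TDE-PH-304 period and for Part A symptoms, Table 14.3.1.1 does not give all-cause subject incidence. It equals or understates it, and the truth lies between the larger of the AE and disease-related percentages for that period and their sum. These bounds assume that no occurrences are held only under the efficacy-endpoint route of 9.1.3. If some are, the truth could exceed the sum. They also need AE percentages restricted to TDE-PH-304, whereas Table 14.3.1.1 adds parent-study time for subjects previously on active drug.

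The size cannot be determined. Appendix D is not in the text reviewed, so the overlapping symptoms cannot be named, although 9.1.3 itself anticipates them. A flat statement that the AE table materially understates these symptoms would go too far. Serious events are not affected.

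**What to change.** In SAP 11.3, map disease-related event symptoms to MedDRA preferred terms and add one supplementary table restricted to the TDE-PH-304 period. For each Appendix D Part A term, flagging those also in Part B, show side by side the number and percentage of subjects with the symptom as an AE, as a disease-related event, and as either. Count each subject once, by previous study and overall. A subject-level union is needed; adding the two percentages would double-count.

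Include any PAH symptoms recorded under the efficacy-endpoint route if TDE-PH-304 collects them, or state that none are collected. The only efficacy measures in protocol 2.2 are the walk test and the Borg score, so this needs a clear statement.

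Footnote Tables 14.3.1.1 and 14.3.1.8 that these terms are split by investigator attribution. Add that the combined table covers TDE-PH-304 only, while Table 14.3.1.1 also includes parent-study active-drug time. Without that note a reader could find a combined percentage below the AE percentage and be misled.

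The cost is symptom coding, one table and two footnotes, with no change to the protocol or to site work. The downside for the sponsor is a somewhat less favourable symptom incidence. The table would be ever/never only, because SAP 11.3 plans no dates or counts from which a rate per patient-year could be formed.

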9.2 Documentation of Adverse Events

An AE or SAE occurring during the study must be documented in the subject's source documents and on the appropriate CRF page. Information relating to the AE such as onset and cessation date and times, intensity, seriousness, relationship to study drug, and outcome will also be documented in the CRF (see Appendix C for definitions). Where possible, AEs should be recorded using standard medical terminology. If several signs or symptoms are clearly related to a medically defined diagnosis or syndrome, the diagnosis or syndrome should be recorded on the CRF page, not the individual signs and symptoms.

All adverse events should be followed until resolution (or return to normal or baseline values), until they are judged by the Investigator to no longer be clinically significant, or for 30 days following discontinuation of UT-15C. All SAEs that occur during the study will be followed until resolution, death, or the subject is lost to follow-up. Supplemental measurements and/or evaluations may be necessary to fully investigate the nature and/or causality of an AE or SAE. This may include additional laboratory tests, diagnostic procedures, or consultation with other healthcare professionals. CRF pages should be updated with any new or additional information as appropriate.

9.3 Reporting Responsibilities of the Investigator

All SAEs, regardless of expectedness or causality, must be reported to the Sponsor by fax or email [REDACTED] within 24 hours of awareness. A completed SAE report form along with any relevant hospital records and autopsy reports should be faxed to the Drug Safety Department at United Therapeutics Corporation. A follow-up SAE report form should be forwarded to the Drug Safety Department at United Therapeutics Corporation within 48 hours of the receipt of any new/updated information. The Investigator must also promptly notify the Investigational Review Board (IRB) or Ethics Committee (EC) of the SAE, including any follow-up information according to the guidelines set forth by the IRB or EC.

9.4 Safety Reports

In accordance with FDA, European, and national regulations, the Sponsor will notify the FDA, other competent authorities, and all participating investigators of any AE that is considered to be possibly attributable to study drug and is both serious and unexpected. The Investigator must report these AEs to their IRB or EC in accordance with applicable national regulations and guidelines set forth by the IRB or EC. If an event listed in Appendix D Part A or B occurs during the conduct of the trial, it will not give rise to submission of an expedited safety report despite being considered serious and possibly attributable to the study drug, unless the United Therapeutics Medical Monitor, responsible for assessing the case considers it to be unusual (e.g., more severe than expected) and therefore reportable. The data regarding such events will always be recorded in the clinical study database, regardless of reportability.

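### Protocol 9.1.3 and 9.4 by default exempt disease-progression events from expedited reporting even when serious and possibly drug-caused, which conflicts with the protocol's own definition of an event expected for UT-15C

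*Protocol*

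**What the plan says.** Protocol 9.4 begins with a general rule. The sponsor must tell the regulators, and every investigator taking part, about "any AE that is considered to be possibly attributable to study drug and is both serious and unexpected".

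The same section then adds a rule based on a list. It covers events named in either Part of Appendix D, and its effect on such an event is this: "it will not give rise to submission of an expedited safety report despite being considered serious and possibly attributable to the study drug". One exception follows: the sponsor's Medical Monitor may find the event unusual, greater severity being the example given, and so make it reportable. The last paragraph of 9.1.3 carries the same rule with the same exception.

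Section 9.1.3 uses the word expected in two senses. Part A of Appendix D holds events expected from progression of the subject's PAH. For the drug, the definition opens "An expected AE for UT-15C is defined as any AE that is defined in terms of nature, severity, or frequency" and then points to two sources, the Investigators' Brochure and Part B. Part A is not named in that definition.

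**The concern.** Expedited reporting normally turns on whether a serious, possibly drug-related event was to be expected from the drug. The list-based sentence lets an event off because it is to be expected from the disease, and it does so after possible drug causation has been conceded. If UT-15C itself caused a deterioration that looked like ordinary PAH worsening, this wording would by default keep the case out of expedited reports.

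The design makes this more than an editorial matter. All subjects receive UT-15C SR, the study is neither randomized nor blinded (Protocol 5.1 to 5.3), and the documents describe no concurrent control and no independent safety committee. Without a control arm, drug-caused worsening is hard to tell from disease progression in aggregate tables, so single cases already judged possibly drug-related carry extra weight. Aggregate looks come with regulatory submissions and as often as yearly (SAP section 5).

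**Working it through.** No arithmetic applies; the check sets the passages side by side.

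Inputs:

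1. General rule (Protocol 9.4, first sentence): notify if possibly attributable, serious and unexpected.
2. Drug expectedness (9.1.3): Investigators' Brochure and Part B.
3. Disease expectedness (9.1.3): Part A.
4. List-based exemption (9.1.3, last paragraph, and 9.4): Part A or Part B, even if serious and possibly attributable.
5. Exception to the exemption (same places): the Medical Monitor considers the event unusual.

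Take an event that is serious and considered possibly attributable to UT-15C, and apply the general rule (with drug expectedness) and the list-based rule in turn:

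| Where the event is listed | Judged unusual? | General rule | List-based rule | Result |
|---|---|---|---|---|
| Part B and the Brochure, whether or not also in Part A | No | Expected for the drug: not expedited | Not expedited | Agree |
| Part A, but not Part B or the Brochure | Yes | Notify | Reportable | Agree |
| Part A, but not Part B or the Brochure | No | Notify | Not expedited | **Conflict** |
| Neither Part, nor the Brochure | Either | Notify | Does not apply | Agree |

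The conflict sits in one row. A Part A event not considered possibly attributable never meets the general rule, so it raises no conflict either.

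The exception does not remove the third row. It asks whether the event is unusual, whereas the general rule asks whether the drug may have caused it. A drug-caused event that resembles ordinary progression can meet the second test and fail the first.

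The recording rule in 9.1.3 offers a comparison. Part A events attributed to progression are kept off the AE pages of the CRF, but that exclusion is lifted when the event is serious or unusual, or when there is a reasonable possibility that study drug caused it. For recording, then, possible drug causation takes an event out of the disease category. For expedited reporting, the exemption stays in place after causation is conceded.

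**The case against.** The strongest reply is that the passages can be read together. Section 9.1.3 calls both classes expected, the first sentence of 9.4 says only unexpected without adding for the drug, and the list-based sentence is a specific exception to a general rule. The wording permits this. It works, however, only by letting expectedness from the disease count as expectedness from the drug, and 9.1.3 keeps those two apart. At the least, the protocol does not say which list governs.

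Several stronger readings are tempting, and the documents do not support them.

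- A reader might infer that such events are never expedited. The Medical Monitor's exception prevents that, and greater severity is given only as an example of what is unusual, so an event of ordinary severity could also qualify.
- A reader might infer from 9.1.3 that events found only in Part A must exist. That section mentions events on both lists and events on Part B only; every Part A term could still also be in Part B. Events only in Part A are plausible but unconfirmed.
- A reader might infer that ethics committees are cut off. Section 9.3 separately requires the investigator to notify the IRB/EC of an SAE promptly, with no condition on expectedness.
- A reader might turn the planned enrolment of about 900 subjects, with at least 36 months each, into a number of unreported cases. The documents give no event rate, so any such count would rest on a guess.

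The other safeguards also stand. All SAEs reach the sponsor within 24 hours whatever their expectedness or causality (9.3), the data always enter the study database (9.4), and annual safety reports go to the authorities and committees that require them, with any further national reporting duties also to be met (12.1).

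**Conclusion.** The point holds in limited form. Sections 9.1.3 and 9.4 give conflicting instructions for a serious event that is possibly attributable to UT-15C, is listed in Part A but not in Part B or the Brochure, and is not judged unusual. The conclusion assumes that unexpected in the first sentence of 9.4 means unexpected for the drug, as the UT-15C definition in 9.1.3 suggests.

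Its practical size depends on how many terms are in Part A alone. Appendix D was not in the text reviewed, so that number is unknown; if it is zero, the reference to Part A in the exemption is redundant for such events. What is at stake is expedited notice to regulators and to investigators at other sites. No endpoint, analysis or data capture is affected. It is a cheap improvement to safety reporting and does not amount to a failure of safety oversight.

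**What to change.** Amend the last paragraph of 9.1.3 and the matching text in 9.4 so that they say the same thing:

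- For serious events considered possibly attributable to UT-15C, limit the exemption from expedited reporting to events expected for UT-15C, meaning those covered by the Investigators' Brochure and Part B.
- State that listing in Part A alone does not exempt a serious event considered possibly attributable to UT-15C; such an event follows the first sentence of 9.4.
- Keep the Medical Monitor's judgement that an event is unusual as an additional trigger for reporting.

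The cost is a two-sentence change in the next amendment and a modest number of additional expedited reports.
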